8.2. Clinical Laboratory Analyses

8.2.1. Overview of Planned Clinical Laboratory Analyses

The safety analyses will be based on the Modified Intent-To-Treat population, for the analysis on all countries overall and on China Modified Intent-To-Treat population for the analysis on China subgroup alone, unless otherwise specified.

Table 8 provides an overview of the planned analyses, with further details of data displays being presented in [Appendix 14: List of Data Displays](#). All the planned study population analyses will be done on all countries overall, and China subgroup alone (with the exception of those displays specified by country).

Table 8 Overview of Planned Clinical Laboratory Analyses

| Endpoint | Absolute | | | | Change from Baseline | | | |
|--|----------|---|------------|---|----------------------|---|------------|---|
| | Summary | | Individual | | Summary | | Individual | |
| | T | F | F | L | T | F | F | L |
| Chemistry | | | | | | | | |
| Laboratory Values | | | | | | | | |
| Clinical Chemistry | Y | | | | Y | | | |
| Clinical Chemistry values outside the normal range | Y | | | Y | | | | |
| Clinical Chemistry change from baseline value relative to the normal range | Y | | | | | | | |
| Clinical Chemistry maximum post-baseline value | | Y | | | | Y | | |
| Clinical Chemistry minimum post-baseline value | | Y | | | | Y | | |
| Hematology | | | | | | | | |
| Hematology | Y | | | | Y | | | |
| Hematology values outside the normal range | Y | | | Y | | | | |

| Endpoint | Absolute | | | | Change from Baseline | | | |
|--|----------|---|------------|---|----------------------|---|------------|---|
| | Summary | | Individual | | Summary | | Individual | |
| | T | F | F | L | T | F | F | L |
| Hematology change from baseline value relative to the normal range | Y | | | | | | | |
| Hematology maximum post-baseline value | | Y | | | | Y | | |
| Hematology minimum post-baseline value | | Y | | | | | Y | |
| Urinalysis | | | | | | | | |
| Urinalysis data | | Y | | | Y | | | |
| Hepatobiliary (Liver) | | | | | | | | |
| Liver Event | | | | | Y | | | |

NOTES:

- T = Table, F = Figures, L = Listings, Y = Yes display generated, PCI = Potential Clinical Importance
- Summary = Represents TFL related to any summaries (i.e. descriptive statistics) of the observed raw data.
- Individual = Represents FL related to any displays of individual subject observed raw data.

8.3. Other Safety Analyses

8.3.1. Overview of Planned Other Safety Analyses

The safety analyses will be based on the Modified Intent-To-Treat population, for the analysis on all countries overall and on China Modified Intent-To-Treat population for the analysis on China subgroup alone, unless otherwise specified.

[Table 9](#) provides an overview of the planned analyses, with further details of data displays being presented in [Appendix 14: List of Data Displays](#). All the planned study population analyses will be done on all countries overall, and China subgroup alone (with the exception of those displays specified by country).

Table 9 Overview of Planned Other Safety Analyses

| Endpoint | Absolute | | | | | | Change from Baseline | | | | | | |
|--------------------------|----------------|---|---|---------|---|------------|----------------------|---|---|---------|---|------------|---|
| | Stats Analysis | | | Summary | | Individual | Stats Analysis | | | Summary | | Individual | |
| | T | F | L | T | F | F | L | T | F | L | T | F | F |
| Vital Signs | | | | | | | | | | | | | |
| Pulse rate | Y | Y | | Y | | | Y | Y | | | Y | | Y |
| Systolic | Y | Y | | Y | | | Y | Y | | | Y | | Y |
| Diastolic blood pressure | Y | Y | | Y | | | Y | Y | | | Y | | Y |
| 12-Lead ECG | | | | | | | | | | | | | |
| QTc(F) | Y | Y | | Y | Y | | | Y | | | Y | Y | |
| QTc(B) | | | | Y | | | | | | | Y | | |
| PR interval | Y | Y | | Y | | | | Y | | | Y | | |
| Heart Rate | Y | Y | | Y | | | | Y | | | Y | | |
| ECG interpretation | | | | Y | | | | | | | | | |
| ECG abnormalities | | | | Y | | | Y | | | | | | |

NOTES :

- T = Table, F = Figure, L = Listing, Y = Yes display generated.
- Stats Analysis = Represents TFL related to any formal statistical analyses (i.e. modelling) conducted.
- Summary = Represents TFL related to any summaries (i.e. descriptive statistics) of the observed raw data.
- Individual = Represents FL related to any displays of individual subject observed raw data.
- All the tables will be presented by treatment group.

8.3.2. Planned Safety Statistical Analyses

| Primary Statistical Analyses | | | | | | | |
|---|--|----------|--|-------------------|---|-----------------------------|-----------|
| Endpoint(s) | | | | | | | |
| 
 • Pulse rate • Systolic • Diastolic blood pressure • QTc(F) • PR interval • Heart Rate | | | | | | | |
| Model Specification | | | | | | | |
| 
 • ANCOVA model • The absolute and change from baseline value of each endpoint will be statistically analysed at each scheduled time point after the start of treatment separately. • Terms fitted in the ANCOVA model will be include: 
 
 Response	: Absolute value or change from baseline value at each scheduled time point.	
 
 Fixed Categorical	:Treatment, Smoking Status(Screening), Country^[1]	
 
 Fixed Continuous Covariates	:Baseline	
 
 • Baseline is defined in Section 10.5.2.1. • Two models will be fitted; one with a response variable of change from baseline and one with the response variable as absolute value. | | Response | : Absolute value or change from baseline value at each scheduled time point. | Fixed Categorical | :Treatment, Smoking Status(Screening), Country ^[1] | Fixed Continuous Covariates | :Baseline |
| Response | : Absolute value or change from baseline value at each scheduled time point. | | | | | | |
| Fixed Categorical | :Treatment, Smoking Status(Screening), Country ^[1] | | | | | | |
| Fixed Continuous Covariates | :Baseline | | | | | | |
| Model Checking & Diagnostics | | | | | | | |
| 
 • Refer to Appendix 12: Model Checking and Diagnostics for Statistical Analyses. | | | | | | | |
| Model Results Presentation | | | | | | | |
| 
 • Treatment group LS mean values and LS mean change from baseline values with associated standard errors will be presented for each scheduled on-treatment time point for each endpoint. • LS mean treatment differences for comparisons will be presented with associated 95 % CIs. • LS mean change from baseline and associated 95 % CIs for pre-dose values at each scheduled time point by treatment group will be presented graphically. | | | | | | | |
| Example SAS Code | | | | | | | |
| Similar to the code in Section 7.2.2.2 | | | | | | | |

Note: [1]: In China subgroup analysis, Country will be removed.

10. APPENDICES

| Section | Appendix |
|---|---|
| RAP Section 4 : Analysis Populations | |
| Section 10.1 | Appendix 1 : Protocol Deviation Management and Definitions for Per Protocol Population |
| RAP Section 5 : General Considerations for Data Analyses & Data Handling Conventions | |
| Section 10.2 | Appendix 2 : Time and Events |
| Section 10.3 | Appendix 3 : Assessment Windows |
| Section 10.4 | Appendix 4 : Treatment States & Phases |
| Section 10.5 | Appendix 5 : Data Display Standards & Handling Conventions 
 • Study Treatment & Sub-group Display Descriptors • Baseline Definitions & Derivations • Reporting Process & Standards |
| Section 10.6 | Appendix 6 : Derived and Transformed Data 
 • General, Study Population & Safety • Efficacy |
| Section 10.7 | Appendix 7 : Premature Withdrawals & Handling of Missing Data 
 • Premature Withdrawals • Handling of Missing Data |
| Section 10.8 | Appendix 8 : Values of Potential Clinical Importance |
| Section 10.9 | Appendix 9 : Multicentre Studies |
| Section 10.10 | Appendix 10 : Examination of Covariates and Subgroups |
| Section 10.11 | Appendix 11 : Multiple Comparisons and Multiplicity |
| Section 10.12 | Appendix 12 : Model Checking and Diagnostics for Statistical Analyses |
| Other RAP Appendices | |
| Section 10.13 | Appendix 13 : Abbreviations & Trade Marks |
| Section 10.14 | Appendix 14 : List of Data Displays |
| Section 10.15 | Appendix 15 : Example Mock Shells for Data Displays |

10.1. Appendix 1: Protocol Deviation Management and Definitions for Per Protocol Population

Protocol deviations identified in this section are those considered to affect the primary outcome of the study. All decisions on whether to exclude a subject or a subject's data from analysis will be made prior to breaking the blind, with the exception of subjects receiving incorrect treatment container. If, after breaking the blind, the container was found to have contained the correct randomised treatment, no data will be excluded from analyses.

10.1.1. Exclusion of Data from Modified Intent-to-treat Analyses

In general, all data recorded for subjects who were randomised and received at least one dose of study medication will be included in Modified ITT analyses. The following deviations will result in exclusion of data from Modified ITT analyses:

If a 23 h or 24 h post-dose FEV1 or FVC assessment is actually performed after the following day's dose, the value will be excluded from Modified ITT analyses.

If a 15 or 30 min, 1, 3, or 6 h FEV1 or FVC assessment is actually performed before dosing, the value will be excluded from Modified ITT analyses.

Derived endpoints will be calculated from remaining assessment values. Exclusion of a value from Modified ITT analyses does not necessarily mean the subject will not have a value for the derived endpoints.

10.1.2. Exclusions of Data from Per Protocol Analyses

Subjects with full protocol deviations identified below will be excluded from the PP population. Subjects with partial protocol deviations will generally be included in the PP population but have data excluded from PP analyses from the time of the deviation onwards. The exception to this is a partial deviation which occurred prior to the start of treatment – in this case the subject will be excluded from the PP population. Subjects with time-point specific deviations will have only the affected data excluded from PP analyses.

10.1.2.1 Inclusion/exclusion/randomisation Criteria Deviations

Failure of criteria will be considered a full protocol deviations as detailed in [Table 10](#):

Table 10 Inclusion/exclusion/randomisation criteria deviations considered to affect the primary outcome

| Reason for exclusion | Full protocol deviation considered to affect primary outcome |
|------------------------------------|--|
| Inclusion criterion | |
| Type of subject | No |
| Informed consent | No |
| Age | Yes |
| Gender | No |
| COPD History | Yes |
| Tobacco Use and Smoking history | Yes |
| Severity of disease | Yes |
| Dyspnoea (mMRC) | Yes |
| Exclusion criterion | |
| Pregnancy | No |
| Asthma | Yes |
| Other respiratory disorders | Yes |
| Other diseases/abnormalities | No |
| Chest X-ray | Yes |
| Contraindications | No |
| Hospitalisation | Yes |
| Lung resection | Yes |
| 12-lead ECG | No |
| Screening labs | No |
| Medication prior to spirometry | Yes |
| Medication prior to screening | Yes |
| Oxygen | Yes |
| Nebulised therapy | No |
| Pulmonary rehabilitation | Yes |
| Drug or alcohol abuse | No |
| Affiliation with investigator site | No |
| Compliance | No |
| Randomisation criterion | |
| Pre-dose 12-Lead ECG at Visit 2 | No |
| COPD exacerbation | Yes |
| ICS | Yes |
| Prohibited Medications | Yes |

10.1.3. Programmed Checks to Identify Non-medication Deviations

The data checks identified in [Table 11](#) will be performed to further identify protocol deviations.

Table 11 Programmed non-medication checks

| Reason for exclusion | Check performed | Deviation Type |
|---|--|--|
| Age | (visit date – date of birth) < 40 at pre-screening | Full |
| Smoking history | number of pack-years < 10 at screening ^[1] or only use a pipe and/or cigar | Full |
| Severity of disease: FEV1/FVC | Pre-salbutamol or Post-salbutamol FEV ₁ /FVC ≥0.7 or any one missing at screening | Full |
| Severity of disease: % predicted | Pre-salbutamol or Post-salbutamol FEVPDPC > 70% or any one missing at screening | Full |
| Dyspnea (mMRC) | mMRC < 2 at screening or missing | Full |
| COPD exacerbation during run-in | Exacerbation onset date between dates of screening and start of treatment | Full |
| Compliance with treatment | Overall compliance < 80 % or > 120 % or missing | Full |
| Incorrect treatment | At any point | Partial; data excluded from start of incorrect treatment onwards |
| Blind broken ^[3] | At any point | Partial; data excluded from date of breaking of blind |
| COPD exacerbation during treatment and not withdrawn | Exacerbation onset date between treatment start and stop date +1 with measurement of primary efficacy endpoint after onset date ^[2] | Partial; data excluded from date of onset onwards |
| Meet other withdrawn criteria defined in the protocol but not withdrawn | Manual Review | Partial; data excluded from date of PD happened. |
| Trough FEV1 outside window | 23 h or 24 h FEV1 assessment outside window of 22.5-24.5h after previous day's dose | Time-point specific |

Note:

1. Pipe and/or cigar use cannot be used to calculate pack-year history.
2. Subject experiences an exacerbation during the treatment period requiring the use of any systemic or oral corticosteroids with prescribed or non-prescribed (self-administered) antibiotics, and/or requiring emergency treatment or hospitalisation. If subjects used either prescribed or non-prescribed (self-administered) antibiotics only for the treatment of exacerbation, they were permitted to remain in the study under PI's discretion according to the study protocol therefore the use of only antibiotics will not be defined as a protocol deviation.
3. Subjects whose blind was broken by someone external to GSK (i.e. site staff).

10.1.4. Programmed Checks to Identify Medication Deviations

Medications will be classified into Respiratory Medication Class (RMC) as identified in concomitant medications part of Section 10.6.3.

Following agreement of the correct classification, medications taken prior to or on-treatment (i.e. medication start date on or before treatment stop date) in the intervals identified in Table 12 will be reviewed to identify data which should be excluded from analysis. If the disallowed medication started within the specified window prior to Visit 2 the deviation will be considered full and the subject will be excluded from the PP population. Otherwise the deviation will be considered partial and the subject's data will be excluded from PP analyses from the start of the disallowed medication onwards.

Table 12 Programmed medication checks

| RMC | Disallowed rule |
|--|--|
| Depot corticosteroids | Started on-treatment; stopped after 12 weeks prior to V1 |
| Systemic, oral, parenteral and intra-articular corticosteroids | Started on-treatment; stopped after 4 weeks prior to V1. |
| Antibiotics ¹ | Stopped after 4 weeks prior to V1, and reason is LRTI ¹ |
| ICS ² | Started on-treatment; stopped after 30 days prior to V1 ² |
| PDE4 inhibitors | Started on-treatment; stopped after 14 days prior to V1 |
| Long-acting anticholinergics | Started on-treatment; stopped after 7 days prior to V1 |
| Xanthines | Started on-treatment; stopped after 12 hours prior to each visit |
| Leukotriene receptor antagonists | Started on-treatment; stopped after 2 days prior to V1 |
| Oral beta-2 agonists – long acting ³ | Started on-treatment; stopped after 2 days prior to V1 |
| Oral beta-2 agonists - short-acting | Started on-treatment; stopped after day of V1 |
| Inhaled beta-2 agonists – long acting ³ | Started on-treatment; stopped after 2 days prior to V1 |
| Nedocromil or sodium cromoglycate | Started on-treatment; stopped after 1 day prior to V1 and route is inhaled |
| Other investigational medication for COPD | Started on-treatment; stopped after 30 days prior to V1 |
| Any investigational medication | 30 days or 5 half lives, whichever is longer |
| Oxygen | Greater than 12 hours a day |
| Herbal medicine for respiratory diseases | Manual Review |

1. All antibiotics will be identified; manual review to identify those with reason for administration of LRTI. After v1, antibiotics used for acute infection <=2weeks is permitted.

2. All ICS will be identified; manual review to identify ICS:

Started but not as switch from ICS/LABA or not within allowed dose range

Dose>1000 mcg fluticasone propionate or equivalent

Stopped with no change to an alternative steroid in the same dose range within 14 days of stopping

Change dose before treatment or change of more than one dose range on the treatment

3. The definition of LABA has now changed and split in to three categories which are now:

'Long-acting beta-2 agonist – Group 1';

'Long-acting beta-2 agonist – Group 2 (Olodaterol or Indacaterol)';
'Long-acting beta-2 agonist – Group 3 (Salmeterol and Formoterol)';

The final decision on exclusion will be made following manual review and will be documented prior to unblinding.

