8. **Lung Resection:** Subjects with lung volume reduction surgery within the 12 months prior to Screening (Visit 1).
9. **12-Lead ECG:** An abnormal and significant ECG finding from the 12-lead ECG conducted at Visit 1, including the presence of a paced rhythm on a 12-lead electrocardiogram (ECG) which causes the underlying rhythm and ECG to be obscured. Investigators will be provided with ECG reviews conducted by a centralized independent cardiologist to assist in evaluation of subject eligibility. Specific ECG findings that precluded subject eligibility are listed in [Appendix 3](#): The study investigator will determine the medical significance of any ECG abnormalities not listed in [Appendix 3](#).
10. **Screening Labs:** Significantly abnormal findings from clinical chemistry and haematology tests at Visit 1.
11. **Medications Prior to Spirometry:** Unable to withhold albuterol/salbutamol for the 4 hour period required prior to spirometry testing at each study visit.

12. Medications Prior to Screening: Use of the following medications according to the following defined time intervals prior to Visit 1; ([Table 1](#))

Table 1 Time Interval for Prohibited Medication Prior to Visit 1

Medication	Time Interval Prior to Visit 1
Depot corticosteroids	12 weeks
Systemic, oral, parenteral (intra-articular) corticosteroids	4 weeks
Antibiotics (for lower respiratory tract infection)	4 weeks
ICS/LABA combination products if ICS/LABA therapy is discontinued completely	30 days
Use of ICS at a dose >1000mcg/day of fluticasone propionate or equivalent ¹	30 days
Initiation or discontinuation of ICS use ¹	30 days
Phosphodiesterase 4 (PDE4) inhibitors (e.g. roflumilast)	14 days
Long-acting anticholinergics (e.g., tiotropium and aclidinium, glycopyrionium)	7 days
Theophyllines ²	12 hours (stable dose of theophylline alone is allowed during the study but must be withheld 12 hours prior to each study visit)
Oral leukotriene inhibitors (zaflurkast, montelukast, zileuton)	48 hours
Oral beta ₂ -agonists	
Long- acting	48 hours
Short –acting	12 hours
Olodaterol and Indacaterol (inhaled long-acting beta ₂ -agonist)	14 days
Salmeterol, formoterol, (inhaled long-acting beta ₂ -agonist)	48 hours
LABA/inhaled corticosteroid (ICS) combination products only if discontinuing LABA therapy and switching to ICS monotherapy ³	48 hours for LABA component
Inhaled sodium cromoglycate or nedocromil sodium	24 hours
Inhaled short acting beta2-agonists ⁴	4 hours

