5.6.1. Permitted Medications and Non-Drug Therapies

The following relevant medications are permitted during this study.

1. Study-provided albuterol/salbutamol for use as relief medication throughout the Run-in and Treatment periods, except in the 4-hour period prior to spirometry testing
2. Theophylline is permitted, provided that the subject is on a stable dose from Screening (Visit 1) and remains on the stable dose throughout the study; however, theophylline must be withheld for 12 hours prior to and during each clinic visit.
3. Ipratropium bromide is permitted, provided that the subject is on a stable dose from Screening (Visit 1) and remains on the stable dose throughout the study, however, ipratropium bromide must be withheld for 4 hours prior to and during each clinic visit.
4. Inhaled corticosteroids at a dose ≤ 1000 mcg/day of fluticasone propionate or equivalent are permitted provided the dose remains consistent as defined in the SPM throughout the study. Any ICS product alone (e.g., fluticasone propionate) cannot be initiated or discontinued within 30 days prior to Visit 1
5. If the subject is on an ICS/LABA product for at least 30 days to Visit 1, the subject may switch to an ICS product alone as long as it does not exceed 1000mcg/day of FP or equivalent, and the dose remains consistent, as defined in the SPM, throughout the study. The switch to ICS alone from an ICS/LABA product must occur at least 48 hours prior to screen visit. Discontinuation of the

ICS/LABA product completely in the absence of starting an ICS alone must occur at least 30 days prior to V1.

6. Mucolytics such as acetylcysteine
7. As-needed oxygen use (i.e., ≤12 hours per day)
8. Medications for rhinitis (e.g., intranasal corticosteroids, antihistamines, cromolyn, nedocromil, nasal decongestants)
9. Influenza vaccination
10. Pneumonia vaccination
11. Antibiotics for short term treatment of acute infection (≤2 weeks)
12. Oral anticholinergic for overactive bladder
13. Pulmonary rehabilitation program in maintenance phase
14. Smoking cessation treatment, including a stable regimen of nicotine replacement
15. Use of positive airway pressure for sleep apnoea

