6.2.4. Spirometry and Reversibility Testing

6.2.4.1. Spirometry

Spirometry measurements will be performed using equipment that meets or exceeds the minimum performance recommendations of the America Thoracic Society (ATS) [Miller, 2005]. All sites will use standardized spirometry equipment provided by an external vendor.

Subjects should wear nose clips while performing spirometry manoeuvres. For FEV₁ and FVC determinations, at least 3 acceptable spirometry efforts (with no more than 8) should be obtained. Acceptable spirometry efforts should have a satisfactory start of test and end of test (i.e., a plateau in the volume-time curve) and be free from artifacts due to cough, early termination, poor effort, obstructed mouthpiece, equipment malfunction, or other reasons [Miller, 2005; Pelligrino, 2005].

The largest FEV₁ and FVC from the 3 acceptable efforts should be recorded, even if they do not come from the same effort

- Spirometry must be performed as detailed in [Table 5](#), initiated between 8.00am and 12.00pm (noon)
- After completing BDI/TDI, SGRQ and CAT assessments
- At Visit1 after withholding COPD medication as indicated in the exclusion criteria [[Section 4.3](#)]
- At Visit 3 through to visit 8 after withholding the morning dose of the double-blind study medication
- At all visits, after withholding the albuterol/salbutamol rescue medication for ≥ 4 hours
- At all clinic visits after refraining from:
 - smoking for 1 hour
 - drinks with high levels of caffeine such as tea and coffee for at least 2 hours

Details regarding the spirometric procedures are provided in the manual provided by the central spirometry vendor.

Post-dose measurements should be made as close as to the scheduled time points as possible (see [Table 5](#) for timings). Details regarding allowable time windows can be found in the SPM.

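### The SAP's Per Protocol medication checks cover on-treatment theophylline but not on-treatment ipratropium, although the protocol sets the same kind of condition on both

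*SAP*

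**What the plan says.** Protocol 5.6.1 lists theophylline and ipratropium one after the other. For the second it says "Ipratropium bromide is permitted, provided that the subject is on a stable dose from Screening (Visit 1") and stays on that dose throughout, with a 4-hour withhold before and during each clinic visit. Theophylline carries the same stability condition with a 12-hour withhold. For salbutamol, protocol 6.2.4.1 requires spirometry at all visits "after withholding the albuterol/salbutamol rescue medication for" at least 4 hours.

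SAP Appendix 1 defines its own scope: "Protocol deviations identified in this section are those considered to affect the primary outcome of the study". Three tables follow.

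- Table 10 covers eligibility and randomisation criteria. Its nearest entry is "Medication prior to spirometry | Yes".
- Table 11 covers non-medication checks. Its one time-point-specific check is "23 h or 24 h FEV1 assessment outside window of 22.5-24.5h after previous day's dose".
- Table 12 covers medication checks. The xanthine rule is "Started on-treatment; stopped after 12 hours prior to each visit". Long-acting anticholinergics have a row, and so do "Oral beta-2 agonists - short-acting". Short-acting anticholinergics, inhaled short-acting beta-agonists and their combination have none.

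The respiratory medication classes in SAP 10.6.2 include short-acting anticholinergics and short-acting beta-2 agonists as separate entries.

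**The concern.** The primary endpoint is pre-bronchodilator trough FEV1, and the Per Protocol repeat is meant to show whether departures from the protocol change the answer. Ipratropium is a bronchodilator of the same pharmacological class as the test drug. The protocol limits its use so that it does not move the trough during the trial. If the Per Protocol rules do not pick up a breach of that limit, the Per Protocol and modified ITT analyses contain the same affected values, and agreement between them says nothing about this breach.

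The SAP gives no reason for treating theophylline and ipratropium differently.

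**Working it through.** **Protocol condition against SAP check**

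| Drug | Protocol condition on treatment | Per Protocol check on treatment |
|---|---|---|
| Theophylline | Stable dose; 12 h withhold | Table 12, xanthine row |
| Long-acting anticholinergic | Prohibited | Table 12 row |
| Ipratropium | Stable dose; 4 h withhold | None |
| Salbutamol | At least 4 h withhold | None at visit level |

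**Could another rule catch an on-treatment ipratropium start?**

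1. The prohibited list (protocol Table 4) does not name short-acting anticholinergics.
2. A start is not a withdrawal criterion in protocol 4.5, so Table 11's row for subjects who met a withdrawal criterion but stayed in does not apply.
3. Ipratropium added for worsening symptoms would meet the exacerbation definition in protocol 6.2.7. Note 2 to Table 11 restricts the exacerbation row to steroids, emergency treatment or hospitalisation.
4. SAP 10.1.4 sends to review the medications that fall in the intervals listed in Table 12. A class without a row has no interval.
5. The modified ITT exclusions in SAP 10.1.1 concern only timing relative to the study dose.

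**Example.** A subject with no other deviation starts ipratropium just after the Day 56 visit. The trough days are 2, 28, 56, 84, 112, 168 and 169. The four later troughs (Days 84, 112, 168 and 169) stay in the Per Protocol model. Had the drug been theophylline, all four would be removed.

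**Are the data there?** Protocol 5.6 has COPD medications recorded in the eCRF with dose, dates and changes, so an ipratropium start or dose change can be programmed. The same section keeps study salbutamol out of the eCRF, and the diary in protocol 6.2.6.1 asks for use over the previous 24 hours without specifying a clock time. A 4-hour salbutamol check therefore has no described data behind it.

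**The plan's own figure.** Inputs from protocol 8.2.1: difference 115 mL, SD 234 mL, 156 and 78 evaluable.

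- SE = 234 × √(1/156 + 1/78) = 32.45 mL.
- Power = Φ(115/32.45 − 1.96) = Φ(1.58) = 94.3%, against the stated 94%.

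The change proposed here alters none of these inputs.

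**Scale, on assumed values only.** Shift in the difference = (excess share of raised troughs on placebo) × (rise per trough). The documents give neither term.

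- Excess of 2 to 10 percentage points, rise of 100 to 200 mL: 0.02 × 100 = 2 mL to 0.10 × 200 = 20 mL, or 2% to 17% of 115 mL.
- Excess of 5 to 15 points, same rise: 5 to 30 mL, or 4% to 26%.
- Equal shares and equal rises: 0 mL. An excess on UMEC reverses the sign.

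**The case against.** **The analysis affected is a secondary line of evidence.** SAP section 4 calls the Per Protocol analysis confirmatory, and SAP 7.1.2 calls it supportive. The modified ITT analysis decides the trial and keeps these values under any Per Protocol rule. This stands, and it limits the importance of the point.

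**Existing handling.** Table 10 treats medication before spirometry as a full deviation. The criterion behind it is "Unable to withhold albuterol/salbutamol for the 4 hour period required prior to spirometry testing at each study visit", so it would be wrong to say that the SAP ignores withholding. It is, however, an eligibility item, concerns salbutamol only, and does not test whether withholding happened at Days 2 to 169. SAP 4.1 also describes deviation tracking under a management plan that is not in these documents, with review before unblinding. That could find cases, but for exclusions it refers back to Appendix 1, which has no rule for them.

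**Not every later trough is contaminated.** The protocol accepts troughs from stable ipratropium users after a 4-hour withhold. Someone who starts on treatment and withholds properly breaks the stability condition, but the trough need not be raised. This stands: the finding is that a stated protocol condition goes unchecked, not that all these values are wrong.

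**The remedy has a cost.** If starts are commoner on placebo, a partial-deviation rule removes more placebo data after randomisation, plausibly from subjects who are worsening. This also stands. The xanthine row already accepts the same trade-off.

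**Day 1 serial FEV1.** A reader might extend the point to rescue use during the 6-hour profile. Those endpoints have no Per Protocol analysis, and SAP 10.11 calls secondary and other comparisons exploratory, so further handling there is a matter of preference. A separate 12-hour theophylline check would largely repeat the xanthine row.

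**Conclusion.** The gap is real and narrow. Table 12 enforces the protocol's condition for theophylline and leaves out the parallel condition for ipratropium, so post-start or post-change troughs remain in the Per Protocol analysis of the primary endpoint. This rests on reading the tables against protocol 5.6.1 and needs no assumption about rates.

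Two stronger readings are tempting. The first is that the treatment difference is understated by some 5 to 30 mL. That figure is a product of assumed rates and rises. It would apply equally to the modified ITT estimate, which the fix leaves alone. The documents support neither a size nor a direction; more use on placebo is plausible but not stated, and equal use would give no bias. The second is that salbutamol carry-over could simply be screened out. As data collection is described, the clock times needed are not specified. They may be collected under the study procedures manual or the spirometry vendor's manual, which are not available here.

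The point is worth acting on because the correction is cheap, not because a large error has been shown.

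**What to change.** Before unblinding:

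1. Add a row to Table 12: *Short-acting anticholinergics (alone or in combination with SABA): started or dose changed after Visit 1*, as a partial deviation, using eCRF COPD-medication dates and doses. Under SAP 10.1.2, a partial deviation before the start of treatment excludes the subject from the Per Protocol population, so a change during run-in would do the same. State which derived class combination products fall into.
2. Where the time of last salbutamol or ipratropium use is available, flag troughs taken inside the protocol's 4-hour withhold as time-point-specific Per Protocol deviations in Table 11. If times were not collected, say that the check cannot be done.
3. If the sponsor prefers no such rule, give the reason for treating ipratropium differently from theophylline.

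The cost is one table row, a conditional check and a sentence of text. Some post-deviation troughs are lost from the supportive analysis, possibly more on placebo. The planned summary of exclusions from the Per Protocol analysis should show the loss under this row by arm, so that any imbalance is visible. The modified ITT primary analysis, sample size and power do not change.
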